7.1. Treatments Administered

This study involves an evaluation of GI transit time in patients who receive galcanezumab 240 mg administered by subcutaneous injection and erenumab 140 mg administered by subcutaneous injection. Both galcanezumab and erenumab will be administered by site staff once with an autoinjector (AI) pen at Visit 3 of the study. [Table CGBC.7.1](#) shows the treatment regimens.

Table CGBC.7.1. Treatment Regimens

Regimen	Dose Day 7 ± 2
Galcanezumab 240 mg	240 mg (2 × 120-mg SC injection)
Erenumab 140 mg	140 mg (2 × 70-mg SC injection)

Abbreviation: SC = subcutaneous.

The investigator or his/her designee is responsible for

- verifying that instructions are followed properly
- maintaining accurate records of study treatment dispensing and collection, and
- at the end of the study, returning all unused medication to Lilly, or its designee, unless the sponsor and sites have agreed that all unused medications are to be destroyed by the site, as allowed by local law.

7.1.1. Packaging and Labeling

Galcanezumab and erenumab will be supplied as an injectable solution in 1-mL, single-dose, prefilled, disposable AI pen. Each AI pen of galcanezumab is designed to deliver 120 mg/mL, and each AI pen of erenumab is designed to deliver 70 mg/mL. All AI pens will be supplied in single pen cartons, with the site to select the appropriate quantity of AI pens, specific to the planned treatment schedule. Two galcanezumab AI pens are needed for the galcanezumab (240 mg) treatment. Two erenumab AI pens are needed for the erenumab (140 mg) treatment.

The commercial products being provided will be labeled with a commercially approved product label. Each commercial product package is to have a “For CT use only” label.

7.1.2. Medical Devices

The commercial medical devices provided for use in the study are AI pens and the SmartPill™ system. The SmartPill™ motility testing system includes the SmartPill™ motility capsule (WMC), the MotiliGI™ software, and the SmartPill™ motility recorder.

7.2. Method of Treatment Assignment

Patients who meet all criteria for enrollment will be randomized to single-blind treatment at Visit 3. Assignment to treatment groups will be determined by a computer-generated random sequence using an interactive web-response system (IWRS).

To achieve between-group comparability, the randomization will be stratified by site, BMI category ($<30 \text{ kg/m}^2$, $\geq 30 \text{ kg/m}^2$), and by baseline migraine frequency (<8 migraine headache days versus ≥ 8 migraine headache days).

7.2.1. Selection and Timing of Doses

The study treatment will be administered only once at Visit 3.

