WMC administration		X ^a		X		
 • Fasting is defined as no food or drink, except water, for at least 8 hours prior to testing. • No alcohol consumption for 24 hours prior to ingesting the WMC and 6 hours after ingestion. • Tobacco use should also be avoided for 8 hours before ingestion and 6 hours after ingestion of the WMC. • Patients will consume a SmartBar immediately before ingesting WMC and will fast for 6 hours following WMC ingestion. • Patients should not sleep for 6 hours after ingesting the WMC.
Assessment that WMC has been expelled			X ^b	X ^b		The recorder will be returned to the site and data will be uploaded and evaluated to confirm WMC expulsion at Visit 3 and between Visits 4 and 5.
Study treatment administered			X			
Procedures						
Informed consent	X					
Inclusion and exclusion criteria	X					
Concomitant medication review	X	X	X	X	X	

Study Period	SP I Screening and Baseline GI Transit Time		SP II Single-Blind Treatment and Post WMC Evaluation			Notes
	V1	V2	V3	V4	V5	
Urine pregnancy test, performed locally	X				X	
Eligible patient randomized via IWRS			X			
Physical examination	X					
Height	X					
Weight	X					
Medical history	X					
Substance use	X		X	X		Substances: alcohol, caffeine, nicotine, tobacco.
Vital signs	X		X	X	X	Includes body temperature, sitting blood pressure, and pulse.
Assessment of migraine and headache days	X					Will be done retrospectively for the previous month.
GI Symptom Rating Scale (GSRS)	X		X	X	X	
Bristol Stool Form Scale	X		X	X	X	
Spontaneous Bowel movement (SBM) frequency evaluation	X		X	X	X	
Adverse events	X	X	X	X	X	

Abbreviations: GI = gastrointestinal; IBS = irritable bowel syndrome; IWRS = interactive web-response system; SP = study period; TT = transit time; V = visit; WMC = wireless motility capsule.

- ^a If the patient meets the requirement of fasting at Visit 1, then Visit 1 and Visit 2 could be combined. Sites must not instruct patients to fast prior to signing the ICF
- ^b An x-ray may be obtained in the event that the expulsion of the WMC cannot be confirmed.

3. Introduction

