6.1. Inclusion Criteria

Patients are eligible to be included in the study only if they meet all of the following criteria at screening:

Patient and Disease Characteristics

- [1] Patients are 18 to 55 years of age (inclusive) at the time of screening.
- [2] Have a diagnosis of migraine (1.1 and 1.2 ICHD), with or without aura, as determined by the study investigator and in consideration of International Headache Society International Classification of Headache Disorders – 3rd edition guidelines (ICHD-3 2018).
- [3] Have a frequency of less than 15 monthly headache days of which up to 14 can be migraine headache days.
- [4] Patients can be on no more than 1 other migraine preventive treatment (except for tricyclic antidepressants and verapamil) as long as:
 - that patient has had a stable dose of the oral migraine preventive treatment for a minimum of 2 monthsor
 - patients that have received onabotulinumtoxinA for a minimum of 2 cycles prior to Visit 1.

Informed Consent and Patient Agreements

- [5] Are able and willing to give signed informed consent.
- [6] Are reliable and willing to follow study procedures.
- [7] Male patients must agree to use a reliable method of birth control during the study as well as for 5 months after dosing with study treatment.
- [8] Women of childbearing potential must test negative for pregnancy at the time of enrollment based on a urine pregnancy test.
- [9] Women of childbearing potential who are abstinent from sexual intercourse must agree to remain abstinent during the study as well as for 5 months after dosing with study treatment.

- [10] Otherwise, women of childbearing potential must agree to use 1 highly effective method of contraception (including a male partner who has had a vasectomy), or a combination of 2 effective methods of contraception during the study as well as for 5 months after dosing with study treatment. Birth control is not required if the female is infertile due to surgical sterilization (hysterectomy, or at least 6 weeks after surgical bilateral oophorectomy or tubal ligation) confirmed by medical history or menopause.
- [11] Agree not to post any personal medical data related to the study or information related to the study on any website or social media site (e.g., Facebook, Twitter, LinkedIn, Google+, etc.) until the entire trial has completed.

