- [29] Known hypersensitivity to monoclonal antibodies or other therapeutic proteins, or to galcanezumab.
- [30] Known allergy to SmartBar ingredients including granola (rolled oats, evaporated cane juice, expeller pressed canola oil, defatted wheat germ, oat flour, brown rice syrup, molasses, salt, natural flavor, soy lecithin), whey crisp, rice syrup, corn syrup, whey protein isolate, invert sugar, puffed wheat, apples, maltodextrin, sorbitol, apple juice concentrate, partially hydrogenated vegetable oil (cottonseed, soybean), honey, natural and artificial flavor, salt, gluten, vanilla.
- [31] Medications known to alter GI transit times including opioids, tricyclic antidepressants, verapamil, and medications that can affect the WMC test such as proton pump inhibitors, are excluded from the study 1 week prior to Visit 2 and at any time after Visit 2. See medication exclusion list for a full list of excluded medications.

Prior/Concurrent Clinical Trial Experience

- [32] Are currently enrolled in any other clinical study involving an investigational product or any other type of medical research judged not to be scientifically or medically compatible with this study.

Other Exclusions

- [33] In the opinion of the investigator, have other issues that would interfere with compliance with the study requirements and completion of evaluations required for this study.

- [34] Are investigator site personnel directly affiliated with this study and/or their immediate families. Immediate family is defined as a spouse, parent, child, or sibling, whether biological or legally adopted.
- [35] Are Lilly employees or are employees of Medtronic.
- [36] Are unwilling or unable to comply with the use of a data collection device to directly record data from the subject.

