8.1. Discontinuation from Study Treatment

8.1.1. *Permanent Discontinuation from Study Treatment*

Possible reasons leading to permanent discontinuation of study treatment:

- **Subject Decision**
 - the patient requests to discontinue study treatment.
- In addition, patients will be discontinued from the study treatment in the following circumstances:
 - WMC retention or aspiration

Patients discontinuing from the study prematurely for any reason should complete AE and other follow-up procedures per Section 2 (Schedule of Activities), Section 9.2 (Adverse Events), and Section 9.4 (Safety) of this protocol.

8.1.2. *Temporary Discontinuation from Study Treatment*

Not applicable.

8.1.3. *Discontinuation of Inadvertently Enrolled Patients*

If the sponsor or investigator identifies a patient who did not meet enrollment criteria and was inadvertently enrolled, then the patient should be discontinued from study treatment unless there are extenuating circumstances that make it medically necessary for the patient to continue study treatment. If the investigator and the sponsor clinical research physician (CRP)/clinical research scientist (CRS) agree it is medically appropriate to continue, the investigator must obtain documented approval from the sponsor CRP/CRS to allow the inadvertently enrolled patient to continue in the study with or without study treatment. Safety follow-up is as outlined in Section 2 (Schedule of Activities), Section 9.2 (Adverse Events), and Section 9.4 (Safety) of the protocol.

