10.1. Sample Size Determination

Assuming within-group mean difference in CTT is about 4.2 hours with standard deviation of approximately 8, a sample of 30 patients in each treatment group will provide 80% power to detect the difference within the treatment group. The total sample size for the study would be 60.

Assuming 20% screen failure rate, approximately 75 patients may be screened to enroll 60 patients into the study. Eligible patients will be randomized in a 1:1 ratio to galcanezumab or erenumab to have about 30 patients in each treatment group.

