10.3. Statistical Analyses

10.3.1. General Statistical Considerations

Statistical analysis of this study will be the responsibility of Lilly or its designee. Details of statistical analysis methods will be described in the statistical analysis plan (SAP).

Unless otherwise specified, analyses will be conducted on the ITT population, which will include all patients who are randomized and receive at least 1 dose of study treatment. Patients in the ITT population will be analyzed according to the treatment group to which they are randomized. When change from baseline is assessed, the patient will be included in the analysis only if the patient has baseline and postbaseline measurements.

Investigative sites with fewer than 4 randomized patients per treatment group will be pooled for statistical analysis purposes.

All tests of within-group and between-group comparisons will be conducted at a 2-sided alpha level of 0.05, unless otherwise stated.

Any change to the data analysis methods described in the protocol will require an amendment ONLY if it changes a principal feature of the protocol. Any other change to the data analysis methods described in the protocol, and the justification for making the change, will be described in the SAP or the clinical study report (CSR). Additional exploratory analyses of the data will be conducted as deemed appropriate.

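### No usable baseline colonic transit time is required before randomisation at Visit 3, and the sample size has no allowance for the patients this removes from the primary analysis

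*Protocol*

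**What the plan says.** **Eligibility and randomisation.** Protocol 6.1 states: "Patients are eligible to be included in the study only if they meet all of the following criteria at screening". Protocol 6.2 applies the exclusions at the same point. The Schedule of Activities (Protocol 2) marks the inclusion and exclusion check at Visit 1 only, and the baseline capsule is swallowed at Visit 2. Protocol 7.2 randomises, at Visit 3, the patients who meet the enrolment criteria. None of those criteria mentions a baseline CTT or a readable recording.

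**Visit 3.** The recorder comes back and "data will be uploaded and evaluated to confirm WMC expulsion at Visit 3". No consequence of that evaluation is given. On dosing, Protocol 7.2.1 says only "The study treatment will be administered only once at Visit 3". The rationale in Protocol Appendix 3 for this wording is that dosing does not hinge on expulsion. Protocol 8.1.1, however, lists "WMC retention or aspiration" among the circumstances in which study treatment is discontinued.

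**Prohibited drugs.** Under exclusion 31, drugs that alter transit or disturb the capsule test "are excluded from the study 1 week prior to Visit 2 and at any time after Visit 2". Concomitant medication is reviewed at every visit.

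**Analysis.** For change from baseline, Protocol 10.3.1 says "the patient will be included in the analysis only if the patient has baseline and postbaseline measurements", and SAP 6.1 says the same. The primary ANCOVA (Protocol 10.3.3.1, SAP 6.10.1) also uses baseline CTT as a covariate. SAP 6.3 deals with missing data only for the repeated-measures models.

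**Sample size.** Protocol 10.1 and SAP 5.2 plan 30 patients per group for 80% power. The only loss they allow for is 20% screen failure, which gives 75 screened for 60 enrolled.

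**The concern.** Study Period I exists largely to obtain the baseline capsule test, yet its result has no stated bearing on who is randomised. If the recording has failed or cannot be read, this can be known at Visit 3 before the patient is assigned. As written, the patient is still randomised, receives a study drug and swallows a second capsule at Visit 4, with no possible contribution to the primary endpoint.

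The timing makes this a practical matter. The recorder is worn for up to 5 days (Protocol 9.1.1). Visit 2 is at Day -7 ± 2, so Visit 3 falls 5 to 9 days later, and a late capsule exit can go unrecorded. The Schedule of Activities allows an x-ray when expulsion cannot be confirmed. An x-ray can show that the capsule has gone, but not when it left, so even confirmed expulsion does not guarantee a CTT.

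At stake are the precision of the two within-group estimates and the stated power. Losses from late exits would also fall on patients with slow transit, in a trial about slowed transit. The documents give nothing from which to size that selection.

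**Working it through.** **Inputs from the documents.** "Assuming within-group mean difference in CTT is about 4.2 hours with standard deviation of approximately 8" (Protocol 10.1, read here as the SD of the within-patient change); 30 patients per group; 20% screen failure. On alpha: "All tests of within-group and between-group comparisons will be conducted at a 2-sided alpha level of 0.05" (Protocol 10.3.1).

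**Assumed input.** The proportion d of randomised patients without a usable baseline CTT. No rate is given, so 5%, 10% and 15% are shown.

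**Step 1: reproduce the stated power.** One-sample t-test on the change, with noncentrality λ = (4.2/8) × √n and n - 1 degrees of freedom. At n = 30, λ = 0.525 × 5.477 = 2.876 and power is 79.4%. The exact t calculation needs n = 31 for 80%; the normal approximation needs 28.5, rounded up to 29. The plan's figure reproduces, but only with all 30 patients per group contributing both CTT values.

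**Step 2: reproduce the screening figure.** 60 / (1 - 0.20) = 75.

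**Step 3: power after loss of baselines, with no gate and no inflation.**

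| d | 60 × (1 - d) with a baseline CTT | n per group used | λ | Power |
|---|---|---|---|---|
| 0% | 60 | 30 | 2.876 | 79.4% |
| 5% | 57 | 28 | 2.778 | 76.4% |
| 10% | 54 | 27 | 2.728 | 74.7% |
| 15% | 51 | 26 | 2.677 | 73.0% |

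At 5% and 15% the count per group is a half (28.5 and 25.5). Taking the other neighbour gives 77.9% at n = 29 and 71.2% at n = 25. The planned ANCOVA pools the residual variance over both groups. With 2n - 6 degrees of freedom (assuming two pooled sites) and the SD left at 8, power is 80.6% with no loss, and 77.8%, 76.2% and 74.6% for n = 28, 27 and 26. The level is about one point higher and the drop is much the same.

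**Step 4: cost of moving the loss before randomisation.** Screened = 60 / (0.8 × (1 - d)):

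- 5%: 60 / 0.76 = 78.9, so 79
- 10%: 60 / 0.72 = 83.3, so 84
- 15%: 60 / 0.68 = 88.2, so 89

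**Step 5: cost of inflating instead.** Randomised per group = 30 / (1 - d): 31.6, 33.3 and 35.3, so 32, 34 and 36.

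**Step 6: the dosing passages side by side.** Protocol 7.2.1 and its Appendix 3 rationale let the only dose go ahead whether or not the capsule is out. Protocol 8.1.1 discontinues study treatment for capsule retention. With a single dose at Visit 3, that rule can affect treatment only if it is applied before the dose. Retention is not defined, and it is not distinguished from a capsule that has simply not yet been expelled.

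**The case against.** **The run-in does carry a live criterion.** A reader might infer that nothing learned between Visits 1 and 3 can stop randomisation. The documents do not support that. Exclusion 31 continues after Visit 2, medication is reviewed at Visit 3, and Protocol Appendix 1 defines enrolment as assignment to treatment. A patient found at Visit 3 to have taken a prohibited drug can be seen to fail it. Such use is also a listed important protocol deviation (SAP Appendix 1), and a population without these patients may be explored. What remains is narrower: the Schedule of Activities has no eligibility check at Visit 3, and the main analysis keeps such a patient if randomised.

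**These patients are not lost to the whole trial.** It is tempting to say they answer none of the transit objectives. Gastric emptying and small bowel transit are measured before the colon, so a capsule still in the colon can give both. Bowel movement counts, GSRS, BSFS and safety data are also kept.

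**Exclusion for an unexpelled capsule is an inference.** A missing baseline CTT is explicitly excluded. For a capsule still inside, the plan does not say whether a truncated CTT counts as missing or receives a value.

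**The sponsor uncoupled dosing from expulsion on purpose.** This stands, and a blanket gate on capsule exit would in effect undo it. But the stated reason concerns dosing and does not address whether the patient has a baseline for the primary endpoint.

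**The harm is mainly precision, and its size is assumed.** This also stands. Baseline loss precedes randomisation, so it cannot depend on treatment. Patients with chronic constipation, IBS or fewer than three bowel movements in the week before Visit 1 are already excluded, which may keep the rate low. The 20% allowance could absorb losses before Visit 3, but only if a rule made an unusable baseline a failure before randomisation. No such rule exists.

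**Conclusion.** The point holds in a limited form. No text requires a usable baseline CTT before randomisation. A patient without one can be randomised and dosed and is then dropped from the primary analysis, with no imputation rule for CTT and no allowance in the sample size. The 80% power has no reserve: two patients lost per group already bring the paired t figure to 76.4%. The 5% to 15% range is illustrative, and the calculation rests on reading 8 hours as the SD of the change.

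The passages on an unexpelled baseline capsule conflict as they stand, or at best leave open whether retention covers it. They need reconciling, and the documents do not settle which should govern. This is a recommended change; it does not invalidate the design.

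**What to change.** 1. In Protocol 7.2 and the Schedule of Activities, add a Visit 3 check before IWRS randomisation that (a) the uploaded baseline recording is readable enough to give a CTT and (b) exclusion 31 was met during the baseline test.
2. Count patients with a failed or unreadable recording as failures before randomisation, and update the estimate of 75 screened using the sponsor's own expected rate (about 79, 84 or 89 at the rates assumed above).
3. Reconcile Protocol 7.2.1, its Appendix 3 rationale and 8.1.1, and define retention as against not yet expelled. The sponsor decides how a patient with an unexpelled baseline capsule is handled. If such patients are randomised, the SAP should say how their CTT is treated, and the number randomised should allow for any who are then excluded.

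**Cost.** A short amendment, a few more patients screened, and a quick look at the recording at Visit 3. The upload is already scheduled there, but for confirming expulsion. The formal reading is done by blinded expert readers through a central reader, so the Visit 3 check must be a simple one ahead of that read, and some recordings that pass may later prove unusable. For failed or unreadable recordings, the check removes only patients whom the complete-pairs rule would drop from the primary analysis anyway, although their symptom and safety data would no longer be collected. It does not protect against a missing Visit 4 CTT, which needs its own allowance.

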7.3. Blinding

This is a single-blind study. Only the investigator, site personnel, and sponsor will know the randomized treatment after randomization. Site Personnel are responsible to ensure patients remain blinded to treatment (i.e., patients must not see the AI pens before, during, or after the drug administration). See the Manual of Operations for further details regarding blinding.

7.4. Dosage Modification

Not applicable.

7.5. Preparation/Handling/Storage/Accountability

The investigator or his/her designee is responsible for the following:

- confirming appropriate temperature conditions have been maintained during transit for all study treatment received and any discrepancies are reported and resolved before use of the study treatment.
- ensuring that only participants enrolled in the study may receive study treatment and only authorized site staff may supply or administer study treatment. All study treatments must be stored in a secure, environmentally controlled, and monitored (manual or automated) area in accordance with the labeled storage conditions with access limited to the investigator and authorized site staff.
- the investigator, institution, or the head of the medical institution (where applicable) is responsible for study treatment accountability, reconciliation, and record maintenance (such as receipt, reconciliation, and final disposition records).

The study treatment must be stored according to the storage requirements printed onto the commercial label.

To administer the galcanezumab or erenumab injections, the investigational sites are to refer to the commercial package insert for the preparation and handling instructions of each study treatment.

